Investigator-Initiated Study Protocol

A **R**andomized, **C**ontrolled, **M**asked (Reading Center) **P**rospective **S**tudy of the **E**ffectiveness and **S**afety of the Ocular **T**herapeutix Dextenza (dexamethasone **O**phthalmic insert) 0.4 mg for the treatment of post-operative inflammation and pain in patients who have undergone **P**hotorefractive **K**eratectomy (PRK)

The **R**ESTORE Study

Compound:

DEXTENZA (dexamethasone ophthalmic insert) 0.4 mg for intracanalicular use

Study Name:

A Randomized, Controlled, Masked (Reading Center) Prospective Study of the Effectiveness and Safety of the Ocular Therapeutix Dextenza (dexamethasone ophthalmic insert) 0.4 mg for the treatment of post-operative inflammation and pain in patients who have undergone Photorefractive Keratectomy (PRK)-The RESTORE Study

Clinical Phase:

Prospective, Randomized, Controlled, Masked Investigator-Initiated Trial

Date of Issue:

December 17, 2019

Primary Investigator:

[name]

Sub Investigator:

[name]

Site Name & Location:

Vance Thompson Vision Center
[name]
Sioux Falls, South Dakota
57108

CLINICAL STUDY PROTOCOL SYNOPSIS

TITLE	A Randomized, Controlled, Masked (Reading Center) Prospective Study of the Effectiveness and Safety of the Ocular Therapeutix Dextenza (dexamethasone ophthalmic insert) 0.4 mg for the treatment of post-operative inflammation and pain in patients who have undergone Photorefractive Keratectomy (PRK)
SITE LOCATION(S)	Vance Thompson Vision Center [name]
PRINCIPAL INVESTIGATOR	[name]
OBJECTIVE(S)	To determine patient preference and treatment outcomes with an intracanalicular dexamethasone (0.4mg) insert compared to standard steroid drop regimen in the contralateral eye following bilateral PRK surgery.
STUDY DESIGN	Prospective Open-label Interventional Study Randomized, self-controlled design in which one eye (Group A) receives Dextenza and the second eye (Group B) receives prednisolone acetate 1% QID 1 week, BID 1 week following bilateral PRK surgery. All eyes will receive topical moxifloxacin QID for one week. Moxifloxacin is used post-op regardless of the research. Post-operative evaluations to be performed on Day 3 and Day 4, Month 1, and Month 3. Phone call survey to be performed on Week 2.
STUDY DURATION	3 months
ESTIMATED STUDY COMPLETION DATE	January 2021
POPULATION	
Sample Size:	N=20 (40 eyes)

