1. INTRODUCTION AND RATIONALE

1.1 Introduction

Photorefractive Keratectomy (PRK) is a well-studied, FDA approved, refractive surgery option for many patients. Post-operatively patients are commonly treated with antibiotic drops for infection prophylaxis, steroid drops for inflammation and corneal haze prevention, and finally NSAIDs (non-steroidal anti-inflammatory drugs) for pain management. Although the types of medications are standardized, there are many different protocols that vary based on surgeon and practice preference.

Post-operative drop regimens frequently induce both concerns and questions for patients undergoing ocular surgery. Poor compliance with post-operative medications can lead to unexpected and or unsatisfactory outcomes. With refractive surgery visual outcomes and safety at such a high level, patient satisfaction and experience can be altered by post-operative convenience.

Dextenza (dexamethasone 0.4mg ophthalmic insert) is a steroid eluting intracanalicular plug approved on-label for the treatment of pain and post-operative inflammation in patients who've undergone ocular surgery. Utilizing Dextenza, in place of ophthalmic steroid drops, will provide patients with a lessened number of post-operative drops which decreases both contamination possibilities and improper drug installation. Dextenza's hydrogel technology is proposed to offer patients a gradual sustained delivery of steroid to the ocular surface which may decrease subjective post-operative pain.

The tear film is a key component in corneal epithelial healing as well as refractive outcomes in PRK. In many studies, inflammation and inflammation markers are a driver to decreasing tear film homeostasis. With an intracanalicular steroid plug there is potential benefit to restoring tear film homeostasis sooner, combined with increased tear volume, leading to improved epithelialization and refractive outcomes. Finally, intracanalicular steroid plugs offer patients a preservative free steroid option to further promote epithelial health by decreasing topical preservatives.

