1.2.1 Rationale for Study Design

This prospective contralateral eye study will compare the outcomes of 20 patients undergoing bilateral PRK. In one eye the patient will receive a topical steroid and the contralateral eye will receive a Dextenza ophthalmic insert. Both eyes will receive a topical antibiotic.

The primary endpoint of patient preference and pain was chosen based on previous studies that have shown decreasing topical medications increases patient satisfaction. Secondary endpoints including SPEED survey and corneal staining were chosen to test the hypothesis of less ocular surface disease with Dextenza. Time to epithelialization will be studied to see the positive or neutral effects of steroid plus punctal occlusion on epithelialization. Finally, the other secondary endpoints are standard measures for PRK.

The study inclusion and exclusion criteria were chosen based on patients who normally would be successful with laser refractive surgery. The study follow-up visits were based on the Vance Thompson Vision standard post-operative follow-up protocols.

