3. STUDY DESIGN

3.1 Study Description and Duration

This prospective, open-label, single-center, randomized, investigator-sponsored clinical study seeks to investigate the outcomes of patients undergoing bilateral PRK surgery with the treatment of a dexamethasone intracanalicular insert compared to topical standard of care steroid. All eyes will receive treatment. Additionally, all eyes will receive topical moxifloxacin QID for 1 week. Moxifloxacin is used post-op regardless of the research.

Twenty patient eyes undergoing bilateral PRK surgery will be randomized to receive either Dextenza (Group A) OR standard of care prednisolone acetate 1% QID for 1 week, BID for 1 week (Group B). The contralateral eye will receive treatment with either Dextenza or topical prednisolone as a comparator based on randomization of first eye to Group A or Group B. Post-operative evaluations to be performed on Day 3, Day 4, phone call survey at Week 2, Month 1, and Month 3.

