4.1.2 Exclusion Criteria

A patient who meets any of the following criteria will be excluded from the study:

- Patients under the age of 18.
- Patients who are pregnant (must be ruled out in women of child-bearing age with pregnancy test).
- Active infectious ocular or systemic disease.
- Patients with active infectious ocular or extraocular disease.
- Patients actively treated with local or systemic immunosuppression including systemic corticosteroids.
- Patients with known hypersensitivity to Dexamethasone.
- Patients with severe disease that warrants critical attention, deemed unsafe for the study by the investigator.
- Patients with a history of ocular inflammation or macular edema.
- Patients with allergy or inability to receive intracameral antibiotic.
- Patients on systemic non-steroidal anti-inflammatory drugs (NSAID) greater than 1,200 mg/day
- Patients with a corticosteroid implant (i.e. Ozurdex).
- Patient with corneal pathology which pre-disposes them to unsatisfactory outcomes.
- Patients who do not have 20/20 snellen visual acuity potential pre-operatively.
- MRSE greater than 6 diopters.
- Greater than 2 diopters anisometropia.

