5. STUDY SCHEDULE OF EVENTS AND VISIT DESCRIPTIONS

5.1 Schedule of Events

Study assessments and procedures are presented by visit in Table 1.

Table 1 Schedule of Events

Study Procedure	Screening/ Baseline	Surgical Visit Day 0	Day 3	Day 4	Day 14	Day 28	3 MTH post-op	Early Terminat ion
Visit	VISIT 1	VISIT 2	VISIT 3	VISIT 4	Phone call 1	VISIT 5	VISIT 6	
Windows for Visits	(Day -30 to -1)				(+/- 2 days)	(+/- 3 days)	(+/- 3 days)	
Inclusion/Exclusion	X							
Informed Consent	X							
Demographics	X							
Medical History and Concurrent Illnesses	X							
Concomitant Medications	X	X	X	X		X	X	
Randomization	X							
Confirm Treatment Group		X						
Uncorrected Distance VA testing	X					X	X	
Manifest Refraction	X					X	X	
BCVA (ETDRS at 4m)	X					X	X	
Corneal Haze (via AS-OCT)	X					X	X	
Intraocular Pressure	X		X	X		X	X	
Corneal Staining	X		X	X		X	X	
Slit Lamp Exam	X		X	X		X	X	
Ophthalmic Examination (dilated fundus exam)	X							
Ocular Pain Assessment	X		X	X	X	X		
SPEED Questionnaire	X					X		
COMTOL Survey						X		
Record any surgical complications		X						
Subject reported AEs prior to or after surgery	X	X	X	X	X	X	X	
Intracanalicular dexamethasone insert*		X						
Prescribe post-operative topical therapy regimen**		X						
Insert Visualization			X	X		X	X	

*Eye Randomized to Group A

**Specific for each eye based on Group A or B

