Medical and Ocular History obtained: The site will ask and document all past Ocular history, relevant medical history and surgical history. A list of current medications, dose, route, start date and indications will be obtained and documented for each subject. There will be a subsequent diagnosis and start date for each medication.

[figure not shown]
BCDVA on ETDRS chart: (manifest refraction performed if vision is worse than 20/20 with current MRx). The BCDVA will be captured on an ETDRS worksheet and calculated

Slit Lamp Examination (SLE): Slit lamp examination will be performed on the study eye and fellow eye of each subject by a masked examiner, and will include assessment of the lids and lashes, conjunctiva, tear film, cornea, anterior chamber, iris, and lens. At the screening/Day 0 visit, and 30 day/exit visit SLE will be performed both prior to and following application of the ELM or Lipiflow.

Corneal Staining: A drop of fluorescein will be instilled on the eye, then the masked examiner will use the cobalt blue filter on the slit-lamp to examine the cornea. A grading scale of 0 to 3 is used to evaluate each of the five areas on the cornea. 0 being no staining to 3 being severe staining. All areas are then added together for a maximum score of 15.

National Eye Institute/Industry Grading System

Score each of 5 areas of the cornea and total score:

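### Section 4.1.2 excludes on an intracameral antibiotic that the protocol mentions nowhere else, and does not clearly cover topical moxifloxacin, which every eye receives

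*Protocol*

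**What the plan says.** Section 4.1.2 of the Protocol lists 15 exclusion criteria, and meeting any one of them excludes the patient. One reads "Patients with allergy or inability to receive intracameral antibiotic". It names a route but no agent.

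Elsewhere the antibiotic is described as follows:

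- Synopsis, Study Design: "All eyes will receive topical moxifloxacin QID for one week". The synopsis entry on dose, route and schedule says the same.
- Section 1.2.1: "Both eyes will receive a topical antibiotic".
- Section 3.1: "all eyes will receive topical moxifloxacin QID for 1 week", followed by "Moxifloxacin is used post-op regardless of the research".
- Section 1.1, as background on PRK: "Post-operatively patients are commonly treated with antibiotic drops for infection prophylaxis".

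For the day of surgery, Table 1 (Section 5.1) and the Visit 2 list (Section 5.2.1) show two items that provide treatment: the dexamethasone insert, and the item "Prescribe post-operative topical therapy regimen".

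**The concern.** An eligibility criterion should match what the patient will be given. This one refers to an injection into the anterior chamber, whereas the trial is of surface laser surgery followed by drops or an intracanalicular insert. The mismatch can lead to error in two directions:

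- **Exclusion for an irrelevant reason.** Inability to receive an intracameral drug has no bearing on whether a patient can use antibiotic drops, yet as written it is a ground for exclusion.
- **No clear exclusion for a relevant one.** A patient hypersensitive to moxifloxacin is not plainly covered, although every eye is assigned that drug for a week. The protocol names no substitute.

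What is at stake is correct and consistent eligibility decisions, and a modest point of patient safety. No statistical quantity depends on it.

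**Working it through.** No arithmetic beyond counting applies. The check sets every statement about an antibiotic, or its route, beside the criterion.

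| Place in the Protocol | Route | Agent named |
|---|---|---|
| Synopsis, Study Design | topical | moxifloxacin |
| Synopsis, dose/route/schedule | topical | moxifloxacin |
| Section 1.1 (background on usual practice) | drops | none |
| Section 1.2.1 | topical | none |
| Section 3.1 | topical | moxifloxacin |
| Section 4.1.2 (the criterion) | intracameral | none |

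1. **Route.** Four places assign the trial's antibiotic (the two synopsis entries, Section 1.2.1 and Section 3.1). All four say topical, and three of them name moxifloxacin. Section 1.1 describes usual practice and is only supporting evidence. The word intracameral occurs once in the document, in the criterion itself.

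2. **Procedures.** Visit 2 lists 6 items. Two provide treatment (the insert and the topical regimen), and 0 of 6 is an intracameral antibiotic. Table 1 has 23 procedure rows, and 0 of 23 is an intracameral antibiotic.

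3. **Coverage of the drug given.** Of the 15 exclusion criteria, 2 concern drug allergy. One names dexamethasone; the other is the criterion at issue. So 0 of 15 names moxifloxacin, which is assigned to 20 patients × 2 eyes = 40 eyes.

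4. **Effect on the comparison.** Each patient contributes one Dextenza eye and one prednisolone eye, and both get the same antibiotic. An unsuitable or substituted antibiotic would therefore reach both eyes of a pair, and the wording gives no reason to expect a difference between groups.

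5. **Number of patients affected.** The protocol gives no rate of antibiotic allergy, so this cannot be computed.

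**The case against.** The strongest reply is that this is one stray word with little practical effect.

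- **Allergy is to an agent, not a route.** An investigator would naturally apply the criterion to the antibiotic the patient is about to receive, and since it names no agent, that reading is open. This is fair, and it is why the criticism is limited to saying that moxifloxacin is not clearly covered. The reading works only if the criterion's one specific word is ignored.
- **Routine care already covers the risk.** Moxifloxacin is given whether or not the patient is in the study, and at baseline "The site will ask and document all past Ocular history, relevant medical history and surgical history". The inclusion criteria also require ability to comply with study procedures. These points stand and make the safety gap small. None of them mentions moxifloxacin allergy, and none corrects the criterion.
- **The procedure lists are not exhaustive.** The bandage contact lens that Section 5.2.2 says is to be removed appears in neither Table 1 nor the Visit 2 list. Absence from those lists alone is therefore weak evidence that no intracameral antibiotic is given. That is right. The stronger evidence is that every description of the antibiotic regimen gives a topical route.
- **No wrongly excluded patient has been shown, and silence on a substitute is not an error.** Both are true. Choosing another antibiotic is ordinary clinical judgement, and the silence is noted here only as context.

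**Conclusion.** The inconsistency is real. A binding exclusion criterion names a route that appears nowhere else in the protocol, and it does not clearly cover the antibiotic assigned to all 40 eyes. It is a wording error in an operative rule, worth correcting but of low severity. The number of patients touched is unknown and probably small, because routine allergy checks would be expected to catch most of those at risk. There is no effect on the between-eye comparison, the sample size or the analysis.

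The conclusion assumes that the synopsis and Section 3.1 describe the intended antibiotic regimen. If the site does give an intracameral antibiotic at PRK, the error lies in the treatment description instead, and that is what would need amending.

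**What to change.** Replace the criterion with: *Known hypersensitivity to, or inability to receive, topical moxifloxacin.* Extending it to other fluoroquinolones is optional and a matter for the investigator's judgement; nothing in the protocol calls for it.

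The cost is one line of eligibility text in an amendment, and possibly a few more patients screened out. If the investigator would rather not lose patients from a study of 20, an alternative is to drop the exclusion and state that a substitute topical antibiotic is to be used in both eyes. That also removes the contradiction and keeps the two eyes of a patient on the same antibiotic.

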4.2 Treatment Logistics and Accountability

4.2.1 Packaging, Labeling, and Storage

Intracanalicular dexamethasone insert must be stored in a secure area accessible only to the Investigator and their designee(s) and refrigerated and stored between 2° C and 8° C. Intracanalicular dexamethasone insert contains 0.4 mg dexamethasone and is designed to provide a sustained and tapered release of therapeutic levels of dexamethasone to the ocular surface for up to 30 days for the reduction of post-surgical inflammation and pain associated with ocular surgery. Dexamethasone is an anti-inflammatory 9-fluoro-glucocorticoid (also termed a glucocorticoid agonist) and is the active ingredient found in MAXIDEX® 0.1% (dexamethasone ophthalmic suspension), which contains approximately 50 µg of dexamethasone per drop.

Study inserts will be supplied by Ocular Therapeutix in a sealed foil pouch containing one intracanalicular dexamethasone insert in a foam carrier.

Study inserts will be shipped to the site via overnight shipping using cold packs to maintain a temperature of 2° to 8° C. The Investigator, or an approved representative (e.g. pharmacist), will ensure that all study drug

inserts are stored in a secured area, under recommended storage conditions and in accordance with applicable regulatory requirements. The shipping box is to be opened and stored immediately at the site in a refrigerator intended for investigational products at a temperature of 2° to 8°C.

When the insert is removed from the refrigerator, it should be visually inspected. Exposure of the insert to temperatures outside these limits is not recommended. Records of actual storage conditions (i.e. temperature log) at the study site must be maintained; and must include a record of the dates, when the refrigerator was checked, the initials of person checking, and the temperature.

4.2.2 Supply and Disposition of Treatments

Study insert will be shipped at a temperature of 2° to 8°C to the investigator as needed during the study.

4.2.3 Treatment Accountability

All study insert accountability records will be kept current.

The investigator will account for all opened and unopened packaging of study inserts. These records will contain the dates, quantity, and study medication

- Inserted in each patient,
- disposed of at the site or returned to Ocular Therapeutix

All accountability records will be made available for inspection by regulatory agency inspectors.

4.3 Concomitant Medications and Procedures

At the discretion of their physician, patients may continue to receive all medications and standard treatments administered for other conditions.

5. STUDY SCHEDULE OF EVENTS AND VISIT DESCRIPTIONS

5.1 Schedule of Events

Study assessments and procedures are presented by visit in Table 1.

Table 1 Schedule of Events

Study Procedure	Screening/ Baseline	Surgical Visit Day 0	Day 3	Day 4	Day 14	Day 28	3 MTH post-op	Early Terminat ion
Visit	VISIT 1	VISIT 2	VISIT 3	VISIT 4	Phone call 1	VISIT 5	VISIT 6	
Windows for Visits	(Day -30 to -1)				(+/- 2 days)	(+/- 3 days)	(+/- 3 days)	
Inclusion/Exclusion	X							
Informed Consent	X							
Demographics	X							
Medical History and Concurrent Illnesses	X							
Concomitant Medications	X	X	X	X		X	X	
Randomization	X							
Confirm Treatment Group		X						
Uncorrected Distance VA testing	X					X	X	
Manifest Refraction	X					X	X	
BCVA (ETDRS at 4m)	X					X	X	
Corneal Haze (via AS-OCT)	X					X	X	
Intraocular Pressure	X		X	X		X	X	
Corneal Staining	X		X	X		X	X	
Slit Lamp Exam	X		X	X		X	X	
Ophthalmic Examination (dilated fundus exam)	X							
Ocular Pain Assessment	X		X	X	X	X		
SPEED Questionnaire	X					X		
COMTOL Survey						X		
Record any surgical complications		X						
Subject reported AEs prior to or after surgery	X	X	X	X	X	X	X	
Intracanalicular dexamethasone insert*		X						
Prescribe post-operative topical therapy regimen**		X						
Insert Visualization			X	X		X	X	

*Eye Randomized to Group A

**Specific for each eye based on Group A or B

5.2 Study Visit Descriptions

5.2.1 Study Procedures

Visit 1: Screening/Baseline (Day -30 to -1)

After the patient has provided informed consent, the following information will be collected:

- Inclusion/exclusion

- Demographics
- Medical History and Concurrent Illnesses
- Concomitant Medications
- Randomization
- Uncorrected Distance visual acuity as measured by ETDRS chart at 4m
- Manifest Refraction
- Best-corrected visual acuity as measured by ETDRS chart at 4m
- Corneal haze (via AS-OCT)
- Intraocular pressure
- Corneal Staining
- Slit Lamp Exam
- Ophthalmic Examination (dilated fundus exam)
- Subject reported AEs prior to or after surgery
- Ocular pain assessment
- Modified Speed questionnaire

Visit 2: Surgical Day 0

- Concomitant medications
- Confirm treatment group
- Record any surgical complications
- Subject reported AEs prior to or after surgery
- Intracanalicular dexamethasone insert
- Prescribe post-operative topical therapy regimen

Visit 3: Day 3

- Concomitant medications
- Intraocular pressure
- Corneal staining
- Slit lamp exam
- Subject reported AEs prior to or after surgery
- Insert visualization
- Ocular pain assessment

Visit 4: Day 4

- Concomitant medications
- Intraocular pressure
- Corneal staining
- Slit lamp exam
- Subject reported AEs prior to or after surgery
- Insert visualization
- Ocular pain assessment

Phone Call 1: Day 14 (+/- 2 days)

- Subject reported AEs prior to or after surgery
- Ocular pain assessment

Visit 5: Day 28 (+/- 3 days)

- Concomitant medications
- Uncorrected Distance visual acuity as measured by ETDRS chart at 4m
- Best-corrected visual acuity as measured by ETDRS chart at 4m
- Manifest refraction
- Corneal haze
- Intraocular pressure
- Corneal staining
- Slit lamp exam
- Subject reported AEs prior to or after surgery
- Insert visualization
- Ocular pain assessment
- Modified Speed questionnaire
- Adapted COMTOL Survey

Visit 6: Month 3 (+/- 3 days)

- Concomitant medications
- Uncorrected Distance visual acuity as measured by ETDRS chart at 4m
- Best-corrected visual acuity as measured by ETDRS chart at 4m
- Manifest refraction
- Corneal haze
- Intraocular pressure
- Corneal staining
- Slit lamp exam
- Subject reported AEs prior to or after surgery
- Insert visualization

Medical and Ocular History obtained: The site will ask and document all past Ocular history, relevant medical history and surgical history. A list of current medications, dose, route, start date and indications will be obtained and documented for each subject. There will be a subsequent diagnosis and start date for each medication.

[figure not shown]
BCDVA on ETDRS chart: (manifest refraction performed if vision is worse than 20/20 with current MRx). The BCDVA will be captured on an ETDRS worksheet and calculated

Slit Lamp Examination (SLE): Slit lamp examination will be performed on the study eye and fellow eye of each subject by a masked examiner, and will include assessment of the lids and lashes, conjunctiva, tear film, cornea, anterior chamber, iris, and lens. At the screening/Day 0 visit, and 30 day/exit visit SLE will be performed both prior to and following application of the ELM or Lipiflow.

Corneal Staining: A drop of fluorescein will be instilled on the eye, then the masked examiner will use the cobalt blue filter on the slit-lamp to examine the cornea. A grading scale of 0 to 3 is used to evaluate each of the five areas on the cornea. 0 being no staining to 3 being severe staining. All areas are then added together for a maximum score of 15.

National Eye Institute/Industry Grading System

Score each of 5 areas of the cornea and total score:

